8.1.6 Consecutive absence seizure freedom based on diary

The number and percentage of study participants with consecutive absence seizure freedom based on diary will be summarized by 6-month period within the Evaluation Period, as defined in [Table 3-4](#) and over the entire Evaluation Period truncated at the scheduled Month 24 YEV for participants who continue in the study beyond 2 years. The latter will additionally include any diary entries collected from the end of the 6-month period Months 19 to 24 up to the Month 24 YEV.

The derivation of consecutive absence seizure freedom based on diary is specified in [Section 3.13.9](#). The number and percentage of study participants who met each individual criterion will be summarized for each relevant period, irrespective of whether the other criteria were met.

In addition, the number and percentage of participants with absence seizure freedom will be summarized cumulatively across all relevant periods ending at Months 19 to 24 . A study participant will be categorized as absence seizure free until the 6-month period in which they are first classified as not absence seizure free. After the recurrence of absence seizures, the participant is classified as not absence seizure free regardless of whether they met the criteria for absence seizure freedom in subsequent 6-month periods.

In all summaries the percentages for absence seizure free, not absence seizure free and Criterion 1 will be based on the number of participants in the SS as the denominator. Percentages for Criterion 2 will be based on the number of participants in the SS who met Criterion 1 at each visit.

8.1.7 Sensitivity analysis of the secondary efficacy variable

8.1.7.1 Absence seizure freedom based on diary with modified criterion based on seizure diary completion (including dropouts)

The number and percentage of study participants who are absence seizure free based on diary will be summarized at 3-month time intervals within the Evaluation Period, as defined in [Table 3-3](#), and over the entire Evaluation Period truncated at the scheduled Month 24 YEV for participants who continue in the study beyond 2 years. The derivation of absence seizure freedom based on diary with modified criterion based on seizure diary completion (including dropouts) is specified in [Section 3.13.6](#). The number and percentage of study participants who met each individual criterion will be summarized, irrespective of whether the other criteria were met. Percentages for absence seizure free, not absence seizure free and Criterion 1 will be based on the number of participants in the SS as the denominator. Percentages for Criteria 2 and 3 will be based on the number of participants in the SS who met Criterion 1 at each visit.

8.1.7.2 Absence seizure freedom based on diary with modified criterion based on seizure diary completion (excluding dropouts)

The number and percentage of study participants who are absence seizure free based on diary will be summarized at 3-month time intervals within the Evaluation Period, as defined in [Table 3-3](#), and over the entire Evaluation Period truncated at the scheduled Month 24 YEV for participants who continue in the study beyond 2 years. The derivation of absence seizure freedom based on diary with modified criterion based on seizure diary completion (excluding dropouts) is specified in [Section 3.13.7](#). The number and percentage of study participants who met each individual criterion will be summarized, irrespective of whether the other criteria were met.

If a study participant discontinues the study during a 3-month period and does not meet Criterion 1 during the period of study discontinuation, the participant will be excluded from this period and all subsequent periods. If a study participant discontinues the study at any time before Month 24, they will not be included in the analysis conducted on the Evaluation Period.

The denominator for the percentages of participants that met Criterion 1 will be based on the number of participants with data in the SS. The denominator for all other percentages for each 3-month period will be based on the number of participants who met Criterion 1 during the period. Similarly, the denominator for percentages for the analysis on the Evaluation Period (truncated at Month 24 YEV) will be the number of participants who did not discontinue the study prior to the Month 24 YEV (or FV).

9 PHARMACOKINETICS AND PHARMACODYNAMICS

Unless otherwise indicated, all PK analyses and listings will be carried out for the PKAS.

9.1 Pharmacokinetics

Brivaracetam plasma concentrations will be summarized descriptively, by modal dose category in the Evaluation Period, at each FEV, YEV, and EDV or FV as applicable. Summaries will include n, geometric mean, geometric 95% CI, geometric coefficient of variation, arithmetic mean, SD, median, minimum, and maximum.

Descriptive statistics will be repeated, separately by modal dose category and categorized age group at EP0132 EV (see [Section 6.1](#)), and by modal dose category and weight at N01269 Baseline (<50kg at Baseline vs >=50kg at Baseline).

The statistics are calculated only if at least 2/3 of the individual data at a specific sampling point are above or equal to the LLOQ.

All samples should be pre-dose but in cases where the sample has been taken post-dose, the sample will be excluded from the summaries.

Plasma sample collection times and concentrations will be listed by study participant and visit including the plasma sample collection date and time, daily dose (mg), previous dose date and time, time since previous dose (hours) and plasma BRV concentration ($\mu\text{g}/\text{mL}$). The previous dose date and time refers to the most recent dose taken prior to the plasma sample collection, in most cases this will be the evening dose taken at home the day before the sample. The time since previous dose will be calculated as the difference between the plasma sampling time and the previous dose time. Daily dose refers to the most recent daily dose in mg prior to the sample as reported in the Study Drug Collection Dispensation and Administration eCRF.

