3.3.10 Calculation of modal dose

Modal dose categories will be calculated across all study days on or after the day of first dose of BRV in EP0132 and up to and including the day of last dose of BRV in the Evaluation Period (excluding the Down-Titration Period). Modal dose is calculated as the most frequently taken daily dose category during this period. Modal dose will be categorized as defined in [Table 3-6](#).

Table 3-6: Dose group definitions for calculation of modal dose

Daily dose category (mg/day) ^a	Equivalent mg/kg/day ^b	Dose group label
>0 to <100	>0.0 to <2.0	>0.0 to <2.0 mg/kg/day
≥100 to < 150	≥2.0 to <3.0	≥2.0 to <3.0 mg/kg/day
≥150 to <200	≥3.0 to <4.0	≥3.0 to <4.0 mg/kg/day
≥200	≥4.0	≥4.0 mg/kg/day

^a Daily dose category is modified for participants weighing less than 50kg.

^b For participants weighing ≥50kg, the dose in mg/kg/day is calculated based on a weight of 50kg. The permitted dose range for all participants is between 1 and 4 mg/kg/day.

To calculate modal dose, the following steps will be applied:

1. The total daily dose in mg/kg/day will be classified into 1 of the above categories on a daily basis
 - All participants are assigned 100 mg/day (or equivalently 2.0 mg/kg/day for study participants weighing less than 50kg) at the EV.
 - At the Telephone Call visit, the dose may be adjusted to 50 to 200mg/day (or equivalently 1.0 to 4.0 mg/kg/day for study participants weighing less than 50kg). This is documented on the Study Drug Dispensation and Administration eCRF. If 'maintain dose' is selected, the dose is continued from the EV. If 'modify dose' is selected then the new dose is documented in mg/day, and will be used to calculate the daily dose in mg/kg/day. It is assumed that any new dose is first taken the morning after it is dispensed.
 - Any subsequent changes to the daily dose in mg/day will be documented on the Study Drug Collection Dispensation and Administration eCRF. If 'maintain dose' is selected, the dose is continued from the 'daily dose at last visit' entered on the eCRF at that visit. If 'modify dose' is selected, then the new dose is documented in mg/day and will be used to calculate the daily dose in mg/kg/day.
 - For participants with body weight <50kg, the total daily dose in mg/kg/day will be the total daily dose in mg divided by the most recently available body weight in kg.
 - For participants with body weight ≥50kg, the total daily dose in mg/kg/day will be the total daily dose in mg divided by 50kg.

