 - Each daily dose will then be classified into 1 of the daily dose categories in mg/kg/day. The total daily dose will be attributed to a specific period (the Evaluation Period and additionally a 3-month period as defined in [Table 3-3](#)).
2. Once all total daily doses are converted to mg/kg/day and classified into 1 of the above categories, the modal dose is the dose category which was most frequent within the specific period. In the event of a tie, the modal dose will be set to the lower of the tied dose categories.

The modal dose category will be calculated for each 3-month period the participant enters regardless of the number of days completed in this period. A participant is considered to enter a

period if the end date of the Evaluation Period is on or after the first day of the relevant 3-month period.

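### SAP 9.1 groups visit-specific trough concentrations by modal dose over the whole Evaluation Period, so samples from participants whose dose changed can be tabulated under a dose not in force at sampling

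*SAP*

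**What the plan says.** SAP 9.1 plans the summary of pre-dose concentrations in these words: "Brivaracetam plasma concentrations will be summarized descriptively, by modal dose category in the Evaluation Period". This is done at every FEV and YEV and at the EDV or FV. The summary is repeated with modal dose category crossed with age group at EP0132 entry and, separately, with weight group (below 50 kg, or 50 kg and above) at N01269 Baseline. Samples taken after the dose are excluded.

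SAP 3.3.10 gives the grouping variable: "Modal dose is calculated as the most frequently taken daily dose category during this period". The period runs from the first EP0132 dose to the last dose in the Evaluation Period, leaving out down-titration. A tie goes to the lower category. A finer version is also derived: "The modal dose category will be calculated for each 3-month period the participant enters regardless of the number of days completed in this period". SAP 9.1 does not call on it.

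The dose at sampling is derived for the PK listing: "Daily dose refers to the most recent daily dose in mg prior to the sample". It is not used in any summary.

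The protocol synopsis and section 4.1 allow dose adjustment at any time from 3 days after study start. SAP 3.8 gives the large variation in a participant's doses as its reason for not presenting outputs by treatment group.

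**The concern.** A table of concentrations by dose category at, say, Month 18 will be read as describing people on that dose at Month 18. SAP 9.1 itself relates each sample to the most recent dose, usually the previous evening's. The modal category answers a different question: which category the participant was in on the most days of the whole period. It can be fixed by dosing long before the sample, or by dosing that had not yet happened.

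A whole-period mode suits an exposure table, where each participant contributes once. It does not suit a measurement tied to one day. If the two doses differ for an appreciable share of a cell, its mean does not describe the labelled dose and its spread includes between-dose variation.

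**Working it through.** The documents give no PK precision or sample-size figure, so there is nothing of the plan's to reproduce. The check applies the SAP 3.3.10 rule to hypothetical dose paths and compares the resulting label with the dose in force on the scheduled sampling days.

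**Inputs**
- Dose categories (SAP Table 3-6): >0 to <2.0, 2.0 to <3.0, 3.0 to <4.0, and 4.0 or more mg/kg/day. At 50 kg or above, mg/day is divided by 50.
- Permitted range (SAP Table 3-6, note b): 1 to 4 mg/kg/day. Starting dose: 100 mg/day, which is 100/50 = 2.0 mg/kg/day.
- Scheduled PK visits (SAP Table 3-5): days 183, 365, 548 and 731.

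**Step 1: label against dose at sampling** (participant of 50 kg or more, days 1 to 731)

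| Path | Days per category | Modal label | Mismatched samples |
|---|---|---|---|
| Worked example: 100 mg/day to day 395, then 200 | 395 at 2.0; 731 − 395 = 336 at 4.0 | 2.0 to <3.0 | Months 18 and 24, taken at 4.0: 4/2 = 2-fold |
| 100 mg/day to day 199, then 200 | 199 at 2.0; 532 at 4.0 | 4.0 or more | Month 6, taken at 2.0: 2-fold |
| 100 mg/day to day 14, 200 to day 399, then 50 | 14 at 2.0; 385 at 4.0; 332 at 1.0 | 4.0 or more | Months 18 and 24, taken at 1.0: 4/1 = 4-fold |

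**Step 2: dependence on later dosing.** SAP 3.3.2 allows truncation at Month 24 only for reporting absence seizure freedom, so the PK label uses the full Evaluation Period. If the worked-example participant stays on 200 mg/day, days at 4.0 first outnumber the 395 days at 2.0 on day 395 + 396 = 791. From then on the label becomes 4.0 or more. The Month 18 and 24 samples are now labelled correctly, and the Month 6 and 12 samples, taken at 2.0, are not. The same Month 6 concentration thus changes column according to how long the participant stays in the study.

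**Step 3: effect on a cell.** Assume that trough is proportional to dose, which the documents do not state. Let a share f of a cell's samples come from a dose r-fold below the label.
- Geometric mean is multiplied by r^(−f).
- Variance on the log scale rises by f(1 − f)(ln r)².
- Geometric CV becomes √(exp[ln(1 + CV²) + f(1 − f)(ln r)²] − 1). A CV of 40% without mixing is assumed for illustration.

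| f | Geometric mean factor, r = 2 | Geometric CV, r = 2 | Geometric mean factor, r = 4 | Geometric CV, r = 4 |
|---|---|---|---|---|
| 10% | 0.93 | 46.0% | 0.87 | 61.6% |
| 25% | 0.84 | 51.9% | 0.71 | 81.4% |
| 50% | 0.71 | 55.5% | 0.50 | 93.6% |

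Example: f = 0.25 and r = 2 gives 2^(−0.25) = 0.84, and √(exp[ln 1.16 + 0.1875 × 0.4805] − 1) = 0.519. Where samples come from a dose above the label, as in the worked example, the factor is the reciprocal: 1/0.841 = 1.19 for f = 25% and r = 2.

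**The case against.** The strongest reply has four parts.

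- **Purpose.** Protocol section 3 lists no PK objective, endpoint or estimand, and protocol 9.4.2 promises only descriptive statistics, with any further PK work under a separate plan. This stands. A reader might infer that a dose-proportionality assessment across age and weight groups is compromised, but neither document plans one.
- **Recoverability.** The PK listing gives daily dose and time since previous dose for every sample, and the exposure listing in SAP 10.1 gives dose level with start dates. This also stands: no information is lost. It does not make the summary tables say what their labels imply.
- **Frequency.** A sample is misplaced only if the category at sampling differs from the modal one. The dose check is at 2 weeks and the first scheduled PK sample is at Month 6. If most changes come early, the two largely agree. This stands, and a reader should not infer that every dose group mixes doses.
- **Weight.** The split at 50 kg by N01269 Baseline weight might be read as another route by which samples enter the wrong dose group. It is not. The mg/kg/day dose behind the modal category already uses the most recent weight for those below 50 kg. Baseline weight only labels the subgroup.

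Consistency with the exposure and adverse event tables, which also use modal dose, is a fair reason to keep the modal-dose version as a secondary display.

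**Conclusion.** The concern holds for the planned summary tables in SAP 9.1. Where a participant's dose category changes, a trough can be tabulated under a dose not in force at sampling: 2-fold in the worked example and up to 4-fold within the permitted range. The grouping and the mismatches follow from the SAP's own rule applied to permitted dose paths. The effect on a cell mean rests on proportionality of trough to dose and on an affected share that the documents do not give, so the figures in Step 3 are a range of possibilities and not an estimate.

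Separately, and of minor weight, participants who grow past 50 kg during at least two years of treatment stay in the below-50 kg subgroup. That is a question of subgroup labelling and causes no mixing of doses.

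The consequence is confined to descriptive PK tables. No test, endpoint or sample size is touched. The change is worth making because it is cheap and the tables would otherwise be easy to misread.

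**What to change.** In SAP 9.1, make the main concentration summary by dose category in force immediately before each sample:

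- Take the most recent daily dose before the sample, as already defined for the listing, and exclude any change made at that visit. SAP 3.3.10 assumes that a new dose is first taken the morning after it is dispensed.
- Convert to mg/kg/day by the existing rule in SAP 3.3.10: most recent weight if below 50 kg, otherwise 50 kg.
- Keep the modal-dose table, if wanted, as secondary and label it as modal dose over the Evaluation Period.
- Optionally, base the 50 kg split on weight at the visit.

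The 3-month modal dose is not a good substitute. By SAP Table 3-5 the scheduled PK visits fall on days 183, 365, 548 and 731, which are only days 3, 5, 8 and 11 of the 3-month periods beginning on days 181, 361, 541 and 721. Most of the days setting that mode would follow the sample.

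The cost is one SAP paragraph, a re-specified table and one derived variable. The listing holds the dose in mg, so the conversion must be applied to each sample. Weight is measured at every PK visit (protocol 8.1.2), so no new data are needed.

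The fix does not remove the width of the categories themselves: with a permitted minimum of 1 mg/kg/day, the lowest one still spans nearly 2-fold. Dose-normalised concentrations could be added if that matters.

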9.2 Pharmacodynamics

Not applicable.

10 SAFETY ANALYSES

10.1 Extent of exposure

The study medication duration for the Evaluation Period will be calculated as the date of the final dose of BRV during the Evaluation Period - the date of the first dose of BRV in EP0132 + 1 day. The Evaluation Period is defined in [Table 3-2](#). The overall duration of BRV for the entire study (including down-titration, if applicable) will be calculated as the date of the final dose of BRV - the date of the first dose of BRV in EP0132 + 1 day, where missing or partial date of last dose is handled as described in [Section 4.1.4.5](#).

Table 10-1: Exposure Duration Categories

Category	Duration
>0 months	≥ 1 day
≥ 3 months	≥ 90 days
≥ 6 months	≥ 180 days
≥ 12 months	≥ 360 days
≥ 18 months	≥ 540 days
≥ 24 months	≥ 720 days

Study medication duration for the Evaluation Period and for the entire study will be summarized descriptively for all participants, based on the SS, where study medication duration will be presented in months (1 month is equal to 30 days). In addition, cumulative exposure duration for the Evaluation Period will be summarized (number and percentage of participants). Percentages will be relative to the number of participants in the SS.

Study medication duration during the Evaluation Period will also be summarized categorically by modal dose category (>0.0 to <2.0 mg/kg/day, ≥ 2.0 to <3.0 mg/kg/day, ≥ 3.0 to <4.0 mg/kg/day, ≥ 4.0 mg/kg/day) and overall, based on the SS. Percentages for the modal dose categories will be relative to the number of participants in each exposure duration category. Percentages for the all participants will be relative to the number of participants in the SS. This table will also include participant years of exposure presented for all participants and by modaldose category. The participant years of exposure presented by modaldose category will be the total participant years of exposure of participants within that modaldose category.

Participant years of exposure will be calculated by summing the exposure duration in days for all participants in the Evaluation Period or in the modal dose category, and dividing the resulting value by 365.25.

BRV dosing occurring in clinic at the EV, MEV, FEV, YEV, UV as applicable, and EDV or FV as applicable will listed, indicating the visit, whether the study drug was administered, the date and time of administration, the medication formulation, and the single dosage amount (in mg or mL as applicable).

The study medication duration during the Evaluation Period and overall will be listed on the SS including the date of first dose of study medication, the date of last dose of study medication, and the study medication duration in months.

In addition, a study participant listing on the SS will be produced displaying the prescribed dose level and the associated modal dose level for each 3 month period and over the entire Evaluation Period. This listing will also include the dose level start date within each applicable period.

10.2 Adverse events

Adverse events will be summarized as reported on the EP0132 eCRF without integration of events from the N01269 analysis database. Any AEs that are ongoing at the time of entry into EP0132 will be entered on the EP0132 AE eCRF.

All AEs in this study will be classified as pre-treatment or treatment-emergent. In the following definitions, first dose of BRV refers to the first dose in EP0132. Pre-treatment AEs are defined as AEs which had an onset date prior to the first dose of BRV. Treatment-emergent adverse events are defined as AEs that had onset on or after the day of first dose of BRV. All summaries of TEAEs will be based on the SS. Summaries of TEAEs will be produced for the Overall Period, the Evaluation Period, and for each 3-month period in the Evaluation Period (as defined in [Table 3-3](#)), more details on the requirements of each period for each summary are provided in [Section 10.2.1](#).

For the reporting of UCB plain language summaries (PLS) additional summaries of TEAEs will be reported based on the SS. These will only be produced for the Overall Period.

For all summaries (with the exception of TEAEs leading to permanent discontinuation of study drug) the intercurrent event of treatment discontinuation is handled by using a while-on-treatment strategy where observation ends 14 days after treatment is stopped. Thus summaries will include all TEAEs with onset on or after the day of the first dose of BRV up to and including the date of last dose of BRV + 14 days, where missing or partial date of last dose is handled as described in [Section 4.1.4.5](#).

The standard AE eCRF has the outcome of “worsened” to be used when there is an increase in the intensity of an AE. The definition of “worsened” is when the AE is still present but at a heightened intensity. The eCRF instructions dictate to complete a new AE screen with the event term of the worsened event.

Note that the outcome of “worsened” is not allowed terminology within the CDISC standards. In the SDTM.AE, the data is mapped to the outcome “Not Recovered/Not Resolved”. The outcome of “Worsened” will be kept in SDTM.SUPPAE.

Treatment-emergent adverse events of interest are a selection of TEAEs identified by UCB to be of interest to BRV, and TEAEs of special interest is a selection of TEAEs that a regulatory authority has mandated be reported on an expedited basis, regardless of the seriousness, expectedness, or relatedness of the AE to the administration of a UCB product/compound. Treatment-emergent adverse events of special interest are defined in the protocol. Adverse events of interest will be identified based on MedDRA search criteria, which are documented outside of the SAP. All AEs which are listed in “BRV List of TEAE Topics of Interest Final 24 Aug 2018.xlsx” document (provided by UCB) and are flagged with “P” or “B” in the appropriate column of the “Key” worksheet of this excel file are AEs of interest for this study. On the “MedDRA 18.1 PTs” worksheet the PTs for each topic of interest are identifiable as those flagged with “X” or “x”. Adverse events of special interest will be identified on the AE eCRF.

The duration of each AE will be calculated as follows: date of outcome – date of onset +1. The duration will not be calculated if either the date of outcome (end date) or date of onset is not fully known.

Dose level at onset will be determined as the most recent daily dose in mg/day prior to the study day of AE onset, as defined in [Section 3.13.13](#).

